5.2.3 Analysis of time to event outcomes

Kaplan-Meier method will be used to plot cumulative event rate of time to first event data. If the Kaplan-Meier curves don't cross, log-rank test will be performed to detect a difference between groups. Cox regression will be performed when the proportional hazards assumption is met and hazard ratio and 95% CI will be estimated.

If the Kaplan-Meier curves cross or the proportional hazards assumption is not satisfied, the win ratio method⁵ will be performed.

5.2.4 Analysis of other secondary outcomes (Exploratory Outcome Analysis)

The post-hoc secondary outcomes were analyzed using the same statistical methods described above unless otherwise specified. Specifically, these exploratory outcomes included: occurrence of medium-to-giant CAAs among all participants (Section 5.2.1, repeated measured binary outcomes); CAL progression among all participants (Section 5.2.1, non-repeated measured binary outcomes); and changes in absolute diameters of LMCA, LAD, LCX, the proximal and middle segments of RCA (Section 5.2.2, repeated measured continuous outcomes).

Considering the low incidence of large/giant CAAs (<1%), between-group RRs and two-sided 95% CIs were estimated from a GLM with a negative binomial distribution and log link, adjusting for the mean baseline z scores. Participants with large/giant aneurysms at baseline were excluded from this analysis.

For analysis of CAL progression in participants with baseline CAL, the model was further adjusted for age, sex, KD type, baseline sodium level, CRP concentration, and white blood cell count. RR and corresponding 95% CI were estimated.

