2.2.3 Exploratory Outcomes

The following exploratory outcomes were added by authors during manuscript drafting or suggested by reviewers during revision.

- 1) Occurrence of medium-to-giant CAAs. CAL classification was based on the maximum z score according to the 2017 American Heart Association guideline². Medium CAA was defined as a maximum z score ≥ 5 to < 10 , and all internal diameters < 8 mm; large or giant CAA was defined as a maximum z score ≥ 10 , or any internal diameter ≥ 8 mm. Data were and will be collected at six time points of illness: enrollment, 2th week (± 2 days), 1th month (± 5 days), 3th month (± 5 days), 6th month (± 5 days) and 12th month (± 5 days), respectively.

(Time Frame: from admission to 12 months of illness) (Type: repeatedly measured binary variable)

- 2) Occurrence of large/giant CAAs. Data were and will be collected at six time points of illness: enrollment, 2th week (± 2 days), 1th month (± 5 days), 3th month (± 5 days), 6th month (± 5 days) and 12th month (± 5 days), respectively.

(Time Frame: from admission to 12 months of illness) (Type: binary variable)

- 3) Occurrence of CAL progression within 3 months of illness onset in all participants and those with CAL at baseline. CAL progression was defined as an increment in the z score ≥ 1 from baseline in any coronary artery (LMCA, LAD, LCX, proximal and middle segments of RCA) at any given time point within 3 months of illness onset.

(Time Frame: from admission to 3 months of illness) (Type: binary variable)

- 4) Changes in absolute diameters of LMCA, LAD, LCX, the proximal and middle segments of

RCA from enrollment. Data were and will be collected at six time points of illness: enrollment, 2th week (± 2 days), 1th month (± 5 days), 3th month (± 5 days), 6th month (± 5 days) and 12th month (± 5 days), respectively.

(Time Frame: from admission to 12 months of illness) (Type: repeatedly measured continuous variable)

3. Study Design

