5.1. Primary Outcome Analysis

5.1.1 ITT analysis of the primary outcome - the primary analysis

The primary analysis will be based on the ITT population as defined above. The primary outcome is a binary outcome: CAL occurs or not within 1 month of illness onset. Since CAL will be repeatedly examined at enrollment, 2 weeks, 1 month, 3 months, 6 months and 12 months respectively, generalized estimating equation (GEE) model will be performed, with treatment, visit and interaction between treatment with visit as fixed effect, patient ID as cluster effect, the mean of 5 coronary artery baseline z scores (described in section 2.2.1) as covariate variable. Risk difference (RD) and two-sided 95% confidence intervals (CI) between the two treatment groups will be estimated from the model using a binomial distribution and identity link function. OR with 95% CI at each time point will be obtained using GEE model with binomial distribution and logit link function. Binomial distribution and log link function will be used to obtain estimation of risk ratio (RR) and 95% CI. Exchangeable correlation structure is assumed for within-group variation for all the GEE models. The P value for the interaction term will be used to determine the statistical significance of the group difference at specific time point.

If the above GEE model does not converge, a poisson distribution will be used for the family function. A negative binomial distribution will be subsequently used for family function in case the GEE model based on poisson distribution does not converge. RD, OR and RR with their 95% CI

estimates will be reported by using identity, logit and log link function, respectively. In the final analysis, a normal family distribution was used because none of the three prespecified distribution models converged. RD and 95% CI estimates were derived using identity link function.

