5.2.1 Analysis of binary outcomes

Repeated measured binary outcomes will be analyzed with the same tactics as that used for the primary outcome.

Non-repeated measured binary outcomes, referring to need for additional treatment or not, will be summarized by number (%) of participants by treatment group. The proportion difference will be tested by χ^2 methods or fisher exact test. If necessary for analysis, OR with their two-sided 95% CIs of the two groups will be derived from logistic regression. RR and 95% CI were also estimated using a binomial regression with log link function.

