5.2.2 Analysis of continuous outcomes

The continuous outcome will be summarized using number of subjects (n), mean, standard deviation (SD), minimum, and maximum by intervention group. The repeated measured outcomes (including changes in z score of LMCA; changes in z score of LAD; changes in z score of LCX; changes in z score of the proximal segment of RCA; changes in z score of the middle segment of RCA) will be analyzed by generalized linear mixed model (GLMM) with intervention, visit and interaction between treatment with visit as fixed effect, patient ID as random effect, their baseline value as covariate variable. The outcomes which are not repeated measures (including change in serum C-reactive protein (CRP) concentration from admission to 72 hours after completion of initial IVIG infusion) will be analyzed by GLM. Gaussian distribution and identity link function will be used in the model. Difference in mean changes of outcome with their two-sided 95% confidence intervals between two groups will be estimated.

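### CAL progression, defined as a rise from baseline z, is analysed in all participants without a baseline z term, and the base model in the baseline-CAL subset is not stated

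*SAP*

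**What the plan says.** **Outcome.** SAP 2.2.3, item 3: "CAL progression was defined as an increment in the z score ≥ 1 from baseline in any coronary artery". Any of five segments counts, at any time point within 3 months of onset. The same section says that the exploratory outcomes were added during manuscript drafting or revision.

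**All participants.** SAP 5.2.4 assigns "CAL progression among all participants (Section 5.2.1, non-repeated measured binary outcomes". For such outcomes 5.2.1 says "The proportion difference will be tested by χ^2 methods or fisher exact test". It adds an odds ratio from logistic regression if needed, and "RR and 95% CI were also estimated using a binomial regression with log link function". No covariate is named.

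**Participants with CAL at baseline.** SAP 5.2.4: "the model was further adjusted for age, sex, KD type, baseline sodium level, CRP concentration, and white blood cell count". The model to which these six terms are added is not identified.

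**Other coronary outcomes.**
- Primary outcome (5.1.1): "the mean of 5 coronary artery baseline z scores (described in section 2.2.1) as covariate variable".
- Changes in z score (5.2.2): "their baseline value as covariate variable". Section 5.2.4 sends changes in absolute diameter to the same methods.
- Medium-to-giant aneurysms (5.2.4): repeated binary route of 5.2.1, which follows the primary analysis and so carries mean baseline z.
- Large or giant aneurysms (5.2.4): "adjusting for the mean baseline z scores", although incidence is below 1%.

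**The concern.** Baseline z enters the definition of progression directly, is recorded for the trial, and is the SAP's usual covariate for coronary outcomes. The continuous change in z is adjusted for its baseline value, but the dichotomised form of that change is not, and no reason is given. If baseline z predicts progression, leaving it out gives a less precise comparison than the data allow.

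The subset wording is a separate defect. The word *further* implies an existing adjustment, but the route used for all participants has none. A reader cannot tell whether the subset model holds six covariates, or six plus mean baseline z. For models chosen after the fact, an unexplained covariate set also invites questions about selection.

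**Working it through.** **1. The plan's own figure.** The SAP gives no rate, power or precision for progression. Its only sample-size figure (3.5) is for the primary outcome: 12.4% against 9.1%, two-sided α 0.05, power 0.80, 1400 per arm.

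n = [1.960·√(2·0.1075·0.8925) + 0.8416·√(0.124·0.876 + 0.091·0.909)]² / 0.033² = 1382 per arm, or 1442 with continuity correction. Power at 1400 is 0.805. The stated figure reproduces, and this point does not affect it.

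**2. Which analyses carry a baseline term.**

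| Outcome | Section | Baseline term |
|---|---|---|
| CAL (primary) | 5.1.1 | mean of 5 z scores |
| Change in z, change in diameter | 5.2.2, 5.2.4 | own baseline value |
| Medium-to-giant aneurysm | 5.2.4 via 5.2.1 | as primary |
| Large or giant aneurysm | 5.2.4 | mean z |
| Progression, all participants | 5.2.4 via 5.2.1 | none |
| Progression, baseline CAL | 5.2.4 | not determinable |

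The covariate-free GLM in 5.1.2.10 is a labelled sensitivity analysis of the primary outcome, so it is not a counter-example.

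**3. Size of the possible loss.** Every input here is an assumption except 1400 per arm, the five segments and the three follow-up echoes within 3 months:
- z scores have unit variance, with correlation 0.5 between segments;
- follow-up z = slope × baseline z + an error with SD 0.7, 60% of whose variance is shared across visits;
- the threshold is placed so that 10% or 25% of controls progress;
- the treated rate is 7.0% or 20.5%, set for about 80% unadjusted power.

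R² is the share of the variance of the progression indicator explained by mean baseline z. The SE of the risk difference falls by 1 − √(1 − R²). At slope 0.3 and a 25% rate, for example, 1 − √(1 − 0.275) = 14.9%.

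| Slope | R² (10% / 25% rate) | SE reduction | Power, unadjusted → adjusted (10%; 25%) |
|---|---|---|---|
| 0.3 | 0.218 / 0.275 | 11.6% / 14.9% | 0.795 → 0.885; 0.782 → 0.890 |
| 0.5 | 0.136 / 0.183 | 7.0% / 9.6% | 0.797 → 0.850; 0.797 → 0.882 |
| 0.7 | 0.058 / 0.084 | 3.0% / 4.3% | 0.810 → 0.838; 0.805 → 0.843 |
| 0.85 | 0.014 / 0.024 | 0.7% / 1.2% | 0.807 → 0.800; 0.805 → 0.818 |
| 1.0 | 0 / 0 | 0 / 0 | 0.818 → 0.818; 0.830 → 0.828 |
| 1.3 | 0.057 / 0.083 | 2.9% / 4.3% | 0.850 → 0.877; 0.838 → 0.855 |

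Each power rests on 400 replicates, so its Monte Carlo error is about √(0.8·0.2/400) = 0.02.

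Below slope 1, regression to the mean makes a low baseline predict progression. Above 1, a high baseline predicts it. Near 1 the two cancel.

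**4. Scale.** The gain shows on the risk difference, on a standardised risk ratio and in power. It does not show in the SE of the log odds ratio, which rises with adjustment (0.1378 to 0.1476 at slope 0.5, 10% rate) even though power also rises. Under the same assumptions, Poisson regression with robust SE left the risk ratio essentially unchanged, and the SE of its log fell by no more than the risk-difference figures.

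**The case against.** The strongest reply is that nothing here is invalid. Randomisation makes the unadjusted comparison unbiased, and its confidence interval already allows for chance imbalance. At 1400 per arm that imbalance is small: the difference between arms in mean baseline z has a standard error of √(2/1400) = 0.038 standard deviations. Adjustment is an efficiency choice. The outcome is post hoc, so a new covariate now cannot restore prespecification. All of this stands. It limits the weight of the point but does not remove the inconsistency, and it is why the unadjusted result should stay on view.

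Three stronger readings are tempting, and the SAP does not support them.
- *Baseline z is a strong covariate and precision is materially lost.* The SAP states neither a progression rate nor any relation between baseline and follow-up z. Regression to the mean and disease severity can offset each other, so the range starts at zero.
- *Baseline z is missing from both progression analyses.* This is certain only for all participants. In the subset, *further* could build on the mean baseline z named in the preceding paragraph, so the text is ambiguous.
- *The two analyses conflict because their covariates differ.* They concern different populations, and covariate adjustment does not by itself change what a risk ratio estimates. The shorter covariate list in 5.1.2.2 belongs to a sensitivity analysis of the primary outcome and does not bind this one.

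**Conclusion.** The point holds as an inconsistency with a possible cost in precision. Progression among all participants has no baseline z term, against the SAP's own practice for its other coronary outcomes. The subset model is not fully specified.

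The cost lies between 0 and about 15% of the SE of the risk difference, or between 0 and about 11 points of power from a base near 80% (0.890 − 0.782 = 0.108). The upper end needs a slope as low as 0.3; from about 0.85 to 1.0 the gain is negligible. These figures rest on the assumptions above and apply to all participants. The subset was not worked, because its base model is unknown.

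There is no bias, and the primary and prespecified secondary outcomes are untouched. Impact is modest.

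**What to change.** In SAP 5.2.4:
1. For both populations, estimate the progression risk ratio from a log-binomial model, or Poisson regression with robust SE if that does not converge, with treatment and the mean baseline z score.
2. State explicitly whether the six-covariate model in the baseline-CAL subset includes baseline z.
3. Keep the unadjusted result and the six-covariate result as sensitivity analyses, and label the change as post hoc.

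The cost is one covariate already in the dataset, a rerun of two models and a few lines of text.

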5.3 Handling of Missing data

Missing baseline covariates will be imputed using simple imputation methods in the covariate adjusted analysis based on the covariate distributions, should the missing values for a particular covariate be less than 5%. For a continuous variable, missing values will be imputed from random values from a permuted normal distribution with mean and SD calculated from the available sample. For a categorical variable, missing values will be imputed from random values from a uniform distribution with probabilities P1, P2, ..., and Pk from the sample. The seed to be used is 20230605. We do not assume the condition that missing of covariate variable at baseline will be over 5%.

6. General Considerations for Data Analyses

SAS (version 9.4) will be used to perform all data analyses and generate majority of data displays. STATA® (version 16.0) or R may also be used for some data analyses and generating statistical graphs. All analyses for the primary and secondary outcome variables will be primarily based on ITT population. Two-side tests and P values will be reported. Regression models for repeated measurement will be used for outcomes that are repeatedly measured, group differences at the prespecified timepoint will be computed and reported.

6.1 Data Summaries

Continuous variables will be summarized according to number of subjects with non-missing data (n), mean, standard deviation (SD), median, minimum, maximum and range interquartile (IQR). The confidence intervals will be reported on summaries of continuous effectiveness variables. Categorical variables will be summarized according to the absolute frequency and percentage of subjects (%) in each category level. The denominator for the percentages is the number of subjects in the treatment arm with data available, unless noted otherwise.

6.2 Graphical Displays

Table 1. Baseline characteristics of patients

Analysis Set: ITT population

Variable	Statistic	Treatment A (N=)	Treatment B (N=)	All (N=)
Gender, n (%)	Female			
	Male			
Age (years)	n			
	Mean (SD)			
	Median (IQR)			
	Min-Max			
Height (cm)	n			
	Mean (SD)			
	Median (IQR)			
	Min-Max			
Weight (kg)	n			
	Mean (SD)			
	Median (IQR)			
	Min-Max			
LMCA	n			
	Mean (SD)			
	Median (IQR)			
	Min-Max			
LAD	n			
	Mean (SD)			
	Median (IQR)			
	Min-Max			
LCX	n			
	Mean (SD)			
	Median (IQR)			

Variable	Statistic	Treatment A (N=)	Treatment B (N=)	All (N=)
	Min-Max			
RCA (prox)	n			
	Mean (SD)			
	Median (IQR)			
	Min-Max			
RCA (mid)	n			
	Mean (SD)			
	Median (IQR)			
	Min-Max			

Table 2. Summary for primary outcomes by generalized estimating equation model
Analysis Set: ITT population

		Participants, No. (%)		Generalized estimating equation model analysis		
Primary outcome	Visit	Treatment A	Treatment B	Risk difference (95% CI)	Odds Ratio (95% CI)	Risk ratio (95% CI)
Covariate unadjusted ^a						
CAL	1 month					
	3 months					
	6 months					
	12 months					
Covariate adjusted ^b						
CAL	1 month					
	3 months					
	6 months					
	12 months					

^aThe GEE model only includes the mean of 5 coronary artery baseline z scores as covariate.

^bThe GEE model was adjusted by including ...as covariates.

Table 3. Subgroup analysis of primary outcome by generalized estimating equation model

Analysis Set: ITT population

			Participants, No. (%)		Generalized estimating equation model analysis		
Primary outcome	Variable	Visit	Treatment A	Treatment B	Risk difference (95%CI)	Odds ratio (95%CI)	Risk ratio (95%CI)
CAL	Age (<=1 year)	1 month					
		3 months					
		6 months					
		12 months					
	Age (>1 year)	1 month					
		3 months					
		6 months					
		12 months					
	Gender (F)	1 month					
		3 months					
		6 months					
		12 months					
	Gender (M)	1 month					
		3 months					
		6 months					
		12 months					
	BMI (I)	1 month					
		3 months					
		6 months					
		12 months					
	BMI (N)	1 month					
		3 months					
		6 months					
		12 months					
	BMI (H)	1 month					
		3 months					
		6 months					

			Participants, No. (%)		Generalized estimating equation model analysis		
Primary outcome	Variable	Visit	Treatment A	Treatment B	Risk difference (95%CI)	Odds ratio (95%CI)	Risk ratio (95%CI)
		12 months					

Table 4. Secondary analysis by generalized estimating equation model
Analysis Set: ITT population

		n, mean (SD)		Generalized estimating equation model analysis	
Secondary outcome	Visit	Treatment A (N=)	Treatment B (N=)	Risk difference (95% CI)	P value
LMCA	1 month				
	3 months				
	6 months				
	12 months				
LAD	1 month				
	3 months				
	6 months				
	12 months				
LCX	1 month				
	3 months				
	6 months				
	12 months				
RCA (prox)	1 month				
	3 months				
	6 months				
	12 months				
RCA (mid)	1 month				
	3 months				
	6 months				
	12 months				

Additional tables will be generated if more analyses are conducted.

7. Study Variable List

Table 1 Variable list

Note: T, text variable; D, The date type; N, Continuous variable; B, binary variable; C, categorical variable

No	Variable	Variable Type	Variable interpretation
1	center	T	Name of center
2	id_center	T	Number of center
3	name_pat	T	Acronym of subject
4	patid	N	Study ID of subject
5	time_start	D	Date of enrollment
6	time_end	D	Date of end
7	investigator		Investigator signature
8	inc_1	B	Meeting the diagnostic criteria of Kawasaki disease
9	inc_2	B	Age ≥ 1 month and weight ≤ 30 kg
10	inc_3	B	Fever ≤ 10 days
11	inc_4	B	All coronary z values are <10 before IVIG administration
12	inc_5	B	Able to complete follow-up
13	inc_6	B	The guardian is fully informed and signs the informed consent
14	exclusion_1	B	Use of hormones or other immunosuppressants 1 month before KD onset
15	exclusion_2	B	Recurrence of KD

16	exclusion_3	B	Body temperature is normal at the time of inclusion ($T \leq 37.5 \geq 24h$)
17	exclusion_4	B	With the following infections: sepsis, septic meningitis, peritonitis, bacterial pneumonia, varicella, and influenza
18	exclusion_5	B	History of serious immune diseases, such as immunodeficiency, or chromosomal abnormalities
19	eligibility	B	Eligibility or not
20	arm	T	Intervention allocation
21	gender	B	Gender
22	birth	D	Date of birth
23	tel	T	Telephone
24	height	N	Height at baseline
25	weight	N	Body weight at baseline
26	id_hospital	T	Hospital admission number
27	date_fisrt_fever	D	Date of first fever
28	date_ivig_on	D	Start date of IVIG administration
29	hour_ivig_on	N	Start time of IVIG administration
30	manifes_fever	B	Clinical feature - fever
31	manifes_fever_days	N	Clinical feature - febrile days
32	manifes_fever_high	N	Clinical feature - maximum heating temperature
33	manifes_conjestion	B	Clinical feature - conjunctivitis
34	manifes_rash	B	Clinical feature - rash
35	manifes_tongue	B	Clinical feature - oral changes
36	manifes_swollen_hand	B	Clinical feature - extremity changes
37	manifes_lymph	B	Clinical feature - cervical lymphadenopathy
38	manifes_crissum	B	Clinical feature - perianal vulva flushing and

			molting
39	maniffes_scar	B	Clinical feature - red and swollen kaba
40	manifes_oth	B	Clinical feature - other
41	manifes_oth_txt	T	Clinical feature - other text
42	a_tempstart	N	Body temperature at IVIG administration begin
43	a_notestart	T	Note of body temperature at IVIG administration begin
44	a_temp0h	N	Body temperature at IVIG administration end
45	a_note0h	T	Note of body temperature at IVIG administration end
46	a_temp6h	N	Body temperature at 6 hours after IVIG administration
47	a_note6h	T	Note of body temperature at 6 hours after IVIG administration
48	a_temp12h	N	Body temperature at 12 hours after IVIG administration
49	a_note12h	T	Note of body temperature at 12 hours after IVIG administration
50	a_temp18h	N	Body temperature at 18 hours after IVIG administration
51	a_note18h	T	Note of body temperature at 18 hours after IVIG administration
52	a_temp24h	N	Body temperature at 24 hours after IVIG administration
53	a_note24h	T	Note of body temperature at 24 hours after IVIG administration
54	a_temp30h	N	Body temperature at 30 hours after IVIG

			administration
55	a_note30h	T	Note of body temperature at 30 hours after IVIG administration
56	a_temp36h	N	Body temperature at 36 hours after IVIG administration
57	a_note36h	T	Note of body temperature at 36 hours after IVIG administration
58	a_temp42h	N	Body temperature at 42 hours after IVIG administration
59	a_note42h	T	Note of body temperature at 42 hours after IVIG administration
60	a_temp48h	N	Body temperature at 48 hours after IVIG administration
61	a_note48h	T	Note of body temperature at 48 hours after IVIG administration
62	a_temp54h	N	Body temperature at 54 hours after IVIG administration
63	a_note54h	T	Note of body temperature at 54 hours after IVIG administration
64	a_temp60h	N	Body temperature at 60 hours after IVIG administration
65	a_note60h	T	Note of body temperature at 60 hours after IVIG administration
66	b1_wbc0	N	White blood cell counts before IVIG administration
67	b1_wbc3d	N	White blood cell counts at 72 hours after IVIG administration
68	b1_wbc6d	N	White blood cell counts at 6 days after IVIG administration

69	b1_wbc9d	N	White blood cell counts at 9 days after IVIG administration
70	b2_neutro0	N	Neutrophil counts before IVIG administration
71	b2_neutro3d	N	Neutrophil counts at 72 hours after IVIG administration
72	b2_neutro6d	N	Neutrophil counts at 6 days after IVIG administration
73	b2_neutro9d	N	Neutrophil counts at 9 days after IVIG administration
74	b3_platelet0	N	Blood platelet before IVIG administration
75	b3_platelet3d	N	Blood platelet at 72 hours after IVIG administration
76	b3_platelet6d	N	Blood platelet at 6 days after IVIG administration
77	b3_platelet9d	N	Blood platelet at 9 days after IVIG administration
78	b4_hemoglob10	N	Hemoglobin before IVIG administration - 1
79	b4_hemoglob20	N	Hemoglobin before IVIG administration - 2
80	b4_hemoglob13d	N	Hemoglobin at 72 hours after IVIG administration - 1
81	b4_hemoglob23d	N	Hemoglobin at 72 hours after IVIG administration - 2
82	b4_hemoglob16d	N	Hemoglobin at 6 days after IVIG administration - 1
83	b4_hemoglob26d	N	Hemoglobin at 6 days after IVIG administration - 2
84	b4_hemoglob19d	N	Hemoglobin at 9 days after IVIG administration - 1

85	b4_hemoglob29d	N	Hemoglobin at 9 days after IVIG administration - 2
86	b4_hemoglobunit	T	Unit of hemoglobin
87	b5_hct0	N	HCT before IVIG administration
88	b5_hct3d	N	HCT at 72 hours after IVIG administration
89	b5_hct6d	N	HCT at 6 days after IVIG administration
90	b5_hct9d	N	HCT at 9 days after IVIG administration
91	b6_crp10	N	CRP before IVIG administration - 1
92	b6_crp20	N	CRP before IVIG administration - 2
93	b6_crp13d	N	CRP at 72 hours after IVIG administration - 1
94	b6_crp23d	N	CRP at 72 hours after IVIG administration - 2
95	b6_crp16d	N	CRP at 6 days after IVIG administration - 1
96	b6_crp26d	N	CRP at 6 days after IVIG administration - 2
97	b6_crp19d	N	CRP at 9 days after IVIG administration - 1
98	b6_crp29d	N	CRP at 9 days after IVIG administration - 2
99	b6_crpunit	T	Unit of CRP
100	b7_saa0	N	Serum amyloid A before IVIG administration
101	b7_saa3d	N	Serum amyloid A at 72 hours after IVIG administration
102	b7_saa6d	N	Serum amyloid A at 6 days after IVIG administration
103	b7_saa9d	N	Serum amyloid A at 9 days after IVIG administration
104	c1_esr0	N	Erythrocyte sedimentation rate (ESR) before IVIG administration
105	c1_esr4	N	Erythrocyte sedimentation rate (ESR) after

			IVIG administration
106	c2_alb0	N	Albumin before IVIG administration
107	c2_alb4	N	Albumin after IVIG administration
108	c3_prealb10	N	Prealbumin before IVIG administration - 1
109	c3_prealb14	N	Prealbumin after IVIG administration - 1
110	c3_prealb20	N	Prealbumin before IVIG administration - 2
111	c3_prealb24	N	Prealbumin after IVIG administration - 2
112	c3_prealb30	N	Prealbumin before IVIG administration - 3
113	c3_prealb34	N	Prealbumin after IVIG administration - 3
114	c3_prealbunit	T	Unit of prealbumin
115	c4_gpt10	N	Glutamic-pyruvic transaminase before IVIG administration - 1
116	c4_gpt14	N	Glutamic-pyruvic transaminase after IVIG administration - 1
117	c4_gpt20	N	Glutamic-pyruvic transaminase before IVIG administration - 2
118	c4_gpt24	N	Glutamic-pyruvic transaminase after IVIG administration - 2
119	c4_gptunit	T	Unit of glutamic-pyruvic transaminase
120	c5_got10	N	Glutamic oxalacetic transaminase before IVIG administration - 1
121	c5_got14	N	Glutamic oxalacetic transaminase after IVIG administration - 1
122	c5_got20	N	Glutamic oxalacetic transaminase before IVIG administration - 2
123	c5_got24	N	Glutamic oxalacetic transaminase after IVIG administration - 2
124	c5_gotunit	T	Unit of glutamic oxalacetic transaminase
125	c6_glucose10	N	Blood glucose before IVIG administration -

			1
126	c6_glucose14	N	Blood glucose after IVIG administration - 1
127	c6_glucose20	N	Blood glucose before IVIG administration - 2
128	c6_glucose24	N	Blood glucose after IVIG administration - 2
129	c6_glucoseunit	T	Unit of blood glucose
130	c7_ckmb10	N	Creatine kinase isoenzyme before IVIG administration - 1
131	c7_ckmb14	N	Creatine kinase isoenzyme after IVIG administration - 1
132	c7_ckmb20	N	Creatine kinase isoenzyme before IVIG administration - 2
133	c7_ckmb24	N	Creatine kinase isoenzyme after IVIG administration - 2
134	c7_ckmb30	N	Creatine kinase isoenzyme before IVIG administration - 3
135	c7_ckmb34	N	Creatine kinase isoenzyme after IVIG administration - 3
136	c7_ckmunit	T	Unit of creatine kinase isoenzyme
137	c8_bnp0	N	B-type natriuretic peptide before IVIG administration
138	c8_bnp4	N	B-type natriuretic peptide after IVIG administration
139	c9_probnp10	N	N-terminal moiety of B-type natriuretic peptide before IVIG administration - 1
140	c9_probnp14	N	N-terminal moiety of B-type natriuretic peptide after IVIG administration - 1
141	c9_probnp20	N	N-terminal moiety of B-type natriuretic peptide before IVIG administration - 2

142	c9_probnp24	N	N-terminal moiety of B-type natriuretic peptide after IVIG administration - 2
143	c9_probnpunit	T	Unit of N-terminal moiety of B-type natriuretic peptide
144	c10_sodium0	N	Sodium before IVIG administration
145	c10_sodium4	N	Sodium after IVIG administration
146	c11_troponin10	N	Serum troponin before IVIG administration - 1
147	c11_troponin14	N	Serum troponin after IVIG administration - 1
148	c11_troponin20	N	Serum troponin before IVIG administration - 2
149	c11_troponin24	N	Serum troponin after IVIG administration - 2
150	c11_troponin30	N	Serum troponin before IVIG administration - 3
151	c11_troponin34	N	Serum troponin after IVIG administration - 3
152	c11_troponin40	N	Serum troponin before IVIG administration - 4
153	c11_troponin44	N	Serum troponin after IVIG administration - 4
154	c11_troponinunit	T	Unit of serum troponin
155	c12_tspot0	N	T-SPOT before IVIG administration
156	c12_tspot4	N	T-SPOT after IVIG administration
157	c13_tbil0	N	Serum total bilirubin before IVIG administration
158	c13_tbil4	N	Serum total bilirubin after IVIG administration

159	c14_tg10	N	Triglyceride before IVIG administration - 1
160	c14_tg14	N	Triglyceride after IVIG administration - 1
161	c14_tg20	N	Triglyceride before IVIG administration - 2
162	c14_tg24	N	Triglyceride after IVIG administration - 1
163	c14_tgunit	T	Unit of Triglyceride
164	c15_tc10	N	Total cholesterol before IVIG administration - 1
165	c15_tc14	N	Total cholesterol after IVIG administration - 1
166	c15_tc20	N	Total cholesterol before IVIG administration - 2
167	c15_tc24	N	Total cholesterol after IVIG administration - 2
168	c15_tcunit	T	Unit of total cholesterol
169	c16_ldl10	N	LDL before IVIG administration - 1
170	c16_ldl14	N	LDL after IVIG administration - 1
171	c16_ldl20	N	LDL before IVIG administration - 2
172	c16_ldl24	N	LDL after IVIG administration - 2
173	c16_ldlunit	T	Unit of LDL
174	c17_dimer10	N	D-dimer before IVIG administration - 1
175	c17_dimer14	N	D-dimer after IVIG administration - 1
176	c17_dimer20	N	D-dimer before IVIG administration - 2
177	c17_dimer24	N	D-dimer after IVIG administration - 2
178	c17_dimer30	N	D-dimer before IVIG administration - 3
179	c17_dimer34	N	D-dimer after IVIG administration - 3
180	c17_dimer40	N	D-dimer before IVIG administration - 4
181	c17_dimer44	N	D-dimer after IVIG administration - 4
182	c17_dimer50	N	D-dimer before IVIG administration - 5
183	c17_dimer54	N	D-dimer after IVIG administration - 5

184	c17_dimerunit	T	Unit of D-dimer
185	c18_pct0	N	Calcitonin before IVIG administration
186	c18_pct4	N	Calcitonin after IVIG administration
187	c19_il60	N	IL-6 before IVIG administration
188	c19_il64	N	IL-6 after IVIG administration
189	c20_tnf0	N	TNF before IVIG administration
190	c20_tnf4	N	TNF after IVIG administration
191	d1_date_ucg0	D	Date of ultrasonic cardiogram before IVIG administration
192	d1_date_ucg5	D	Date of ultrasonic cardiogram at 2 weeks of KD onset
193	d1_date_ucg6	D	Date of ultrasonic cardiogram at 1 month of KD onset
194	d1_date_ucg2m	D	Date of ultrasonic cardiogram at 2 months of KD onset
195	d1_date_ucg7	D	Date of ultrasonic cardiogram at 3 months of KD onset
196	d1_date_ucg8	D	Date of ultrasonic cardiogram at 6 months of KD onset
197	d1_date_ucg9	D	Date of ultrasonic cardiogram at 12 months of KD onset
198	d2_lmca0	N	LMCA in ultrasonic cardiogram before IVIG administration
199	d2_lmca5	N	LMCA in ultrasonic cardiogram at 2 weeks of KD onset
200	d2_lmca6	N	LMCA in ultrasonic cardiogram at 1 month of KD onset
201	d2_lmca2m	N	LMCA in ultrasonic cardiogram at 2 months of KD onset

202	d2_lmca7	N	LMCA in ultrasonic cardiogram at 3 months of KD onset
203	d2_lmca8	N	LMCA in ultrasonic cardiogram at 6 months of KD onset
204	d2_lmca9	N	LMCA in ultrasonic cardiogram at 12 months of KD onset
205	d3_lad0	N	LAD in ultrasonic cardiogram before IVIG administration
206	d3_lad5	N	LAD in ultrasonic cardiogram at 2 weeks of KD onset
207	d3_lad6	N	LAD in ultrasonic cardiogram at 1 month of KD onset
208	d3_lad2m	N	LAD in ultrasonic cardiogram at 2 months of KD onset
209	d3_lad7	N	LAD in ultrasonic cardiogram at 3 months of KD onset
210	d3_lad8	N	LAD in ultrasonic cardiogram at 6 months of KD onset
211	d3_lad9	N	LAD in ultrasonic cardiogram at 12 months of KD onset
212	d4_lcx0	N	LCX in ultrasonic cardiogram before IVIG administration
213	d4_lcx5	N	LCX in ultrasonic cardiogram at 2 weeks of KD onset
214	d4_lcx6	N	LCX in ultrasonic cardiogram at 1 month of KD onset
215	d4_lcx2m	N	LCX in ultrasonic cardiogram at 2 months of KD onset
216	d4_lcx7	N	LCX in ultrasonic cardiogram at 3 months

			of KD onset
217	d4_lcx8	N	LCX in ultrasonic cardiogram at 6 months of KD onset
218	d4_lcx9	N	LCX in ultrasonic cardiogram at 12 months of KD onset
219	d5_rca_prox0	N	Proximal segment of RCA in ultrasonic cardiogram before IVIG administration
220	d5_rca_prox5	N	Proximal segment of RCA in ultrasonic cardiogram at 2 weeks of KD onset
221	d5_rca_prox6	N	Proximal segment of RCA in ultrasonic cardiogram at 1 month of KD onset
222	d5_rca_prox2m	N	Proximal segment of RCA in ultrasonic cardiogram at 2 months of KD onset
223	d5_rca_prox7	N	Proximal segment of RCA in ultrasonic cardiogram at 3 months of KD onset
224	d5_rca_prox8	N	Proximal segment of RCA in ultrasonic cardiogram at 6 months of KD onset
225	d5_rca_prox9	N	Proximal segment of RCA in ultrasonic cardiogram at 12 months of KD onset
226	d6_rca_mid0	N	Middle segment of RCA in ultrasonic cardiogram before IVIG administration
227	d6_rca_mid5	N	Middle segment of RCA in ultrasonic cardiogram at 2 weeks of KD onset
228	d6_rca_mid6	N	Middle segment of RCA in ultrasonic cardiogram at 1 month of KD onset
229	d6_rca_mid2m	N	Middle segment of RCA in ultrasonic cardiogram at 2 months of KD onset
230	d6_rca_mid7	N	Middle segment of RCA in ultrasonic cardiogram at 3 months of KD onset

231	d6_rca_mid8	N	Middle segment of RCA in ultrasonic cardiogram at 6 months of KD onset
232	d6_rca_mid9	N	Middle segment of RCA in ultrasonic cardiogram at 12 months of KD onset
233	e1_ecg0	C	ECG before IVIG administration
234	e1_ecg_txt0	T	Text of ECG before IVIG administration
235	e1_ecg1	C	ECG after IVIG administration
236	e1_ecg_txt1	T	Text of ECG after IVIG administration
237	e2_xray0	C	X-ray before IVIG administration
238	e2_xray_txt0	T	Text of X-ray before IVIG administration
239	e2_xray1	C	X-ray after IVIG administration
240	e2_xray_txt1	T	Text of X-ray after IVIG administration
241	e3_mra0	C	MRA before IVIG administration
242	e3_mra_txt0	T	Text of MRA before IVIG administration
243	e3_mra1	C	MRA after IVIG administration
244	e3_mra_txt1	T	Text of MRA after IVIG administration
245	e4_mpi0	C	Myocardial perfusion imaging before IVIG administration
246	e4_mpi_txt0	T	Text of myocardial perfusion imaging before IVIG administration
247	e4_mpi1	C	Myocardial perfusion imaging after IVIG administration
248	e4_mpi_txt1	T	Text of myocardial perfusion imaging after IVIG administration
249	ae	B	Adverse events
250	f1_infection	B	Serious infection
251	f1_infection_hour	N	Occurrence time of serious infection
252	f1_infection_duration	N	Duration of serious infection
253	f1_infection_relation	C	Relation between serious infection and

			drugs
254	f1_infection_intensity	C	Intensity of serious infection
255	f1_infection_treat	C	Treatment of serious infection
256	f1_infection_dose	N	Dose adjustment of serious infection
257	f1_infection_t1	T	Time to start the adjustment of serious infection
258	f1_infection_t2	T	Time to end the adjustment of serious infection
259	f1_infection_outcome	N	Outcome of serious infection
260	f2_skin	B	Skin allergy
261	f2_skin_hour	N	Occurrence time of skin allergy
262	f2_skin_duration	N	Duration of skin allergy
263	f2_skin_relation	C	Relation between skin allergy and drugs
264	f2_skin_intensity	C	Intensity of skin allergy
265	f2_skin_treat	C	Treatment of skin allergy
266	f2_skin_dose	N	Dose adjustment of skin allergy
267	f2_skin_t1	D	Time to start the adjustment of skin allergy
268	f2_skin_t2	D	Time to end the adjustment of skin allergy
269	f2_skin_outcome	C	Outcome of skin allergy
270	f3_heartfailure	B	Heart failure
271	f3_heartfailure_hour	N	Occurrence time of heart failure
272	f3_heartfailure_duration	N	Duration of heart failure
273	f3_heartfailure_relation	C	Relation between heart failure and drugs
274	f3_heartfailure_intensity	C	Intensity of heart failure
275	f3_heartfailure_treat	C	Treatment of heart failure
276	f3_heartfailure_dose	N	Dose adjustment of heart failure
277	f3_heartfailure_t1	D	Time to start the adjustment of heart failure
278	f3_heartfailure_t2	D	Time to end the adjustment of heart failure

279	f3_heartfailure_outcome	C	Outcome of heart failure
280	f4_thromb	B	Thrombogenesis
281	f4_thromb_hour	N	Occurrence time of thrombogenesis
282	f4_thromb_duration	N	Duration of thrombogenesis
283	f4_thromb_relation	C	Relation between thrombogenesis and drugs
284	f4_thromb_intensity	C	Intensity of thrombogenesis
285	f4_thromb_treat	C	Treatment of thrombogenesis
286	f4_thromb_dose	N	Dose adjustment of thrombogenesis
287	f4_thromb_t1	D	Time to start the adjustment of thrombogenesis
288	f4_thromb_t2	D	Time to end the adjustment of thrombogenesis
289	f4_thromb_outcome	C	Outcome of thrombogenesis
290	f5_hypertension	B	Hypertension
291	f5_hypertension_hour	N	Occurrence time of hypertension
292	f5_hypertension_duration	N	Duration of hypertension
293	f5_hypertension_relation	C	Relation between hypertension and drugs
294	f5_hypertension_intensity	C	Intensity of hypertension
295	f5_hypertension_treat	C	Treatment of hypertension
296	f5_hypertension_dose	N	Dose adjustment of hypertension
297	f5_hypertension_t1	D	Time to start the adjustment of hypertension
298	f5_hypertension_t2	D	Time to end the adjustment of hypertension
299	f5_hypertension_outcome	C	Outcome of hypertension
300	f6_othae	B	Other adverse events
301	f6_othae_txt	T	Text of other adverse events
302	f6_othae_hour	N	Occurrence time of other adverse events

303	f6_othae_duration	N	Duration of other adverse events
304	f6_othae_relation	C	Relation between other adverse events and drugs
305	f6_othae_intensity	C	Intensity of other adverse events
306	f6_othae_treat	C	Treatment of other adverse events
